1.1. Subjects

A total of 20 subjects were recruited for this study (9 male, 11 female, average age: 34 ± 10 years). Participants were students and staff members of the Department of Agricultural, Food, Environmental and Animal Sciences at Udine University, Italy. The inclusion criteria were: age between 18-59 years old, good general oral health (self-reported), normal smell and taste functions (self-reported), absence of mastication and/or swallowing problems, normal body mass index (BMI 18.5-24.9 kg/m²) (based on self-reported weight and height) and absence of any food allergy or intolerance for gluten. All participants gave written informed consent. The study was approved by the ethical committee of the University of Udine (protocol number: 0002491).

1.2. Bread products

A 2x3 full factorial design was used with 2 white sandwich breads (a regular gluten-containing (GC) and a gluten-free version (GF)) and 3 spread conditions (no spread, butter and mayonnaise). The breads were commercial products kindly provided by Barilla (Parma, Italy) and Nove Alpi (Pistoia, Italy). The composition of each bread is listed in table 1.

Table 1. Ingredients and nutritional information of studied gluten-free and gluten-containing bread available on the package.

Bread	Ingredients	Energy (kcal)	Total fat (g)	Saturated fat (g)	Total carbo hydrates (g)	Sugar (g)	Fibre (g)	Protein (g)	Salt (g)
Gluten-containing	Wheat flour type "0" (70.6%), water, extra virgin olive oil (2.4%), yeast, salt, sugar, malted barley flour	272	3.9	0.6	48.4	7.3	4.5	8.5	1.25
Gluten-free	Water, corn starch, rice flour, high oleic sunflower oil, yeast, dextrose, thickeners: guar-hydroxypropylmethyl cellulose, iodized salt, soy protein, rice protein, psyllium fiber, quinoa flour, corn flour, aroma	247	5.0	0.55	44.5	3.5	6.0	3.0	1.4

Bread samples were served as two stacked cylinders resembling the consumption of a sandwich (diameter: 3.5 cm, approximate total height: 2.4 cm) (Figure 1). Due to differences in bread density, the average weight of two stacked cylinders was 5.1 ± 0.2 and 5.7 ± 0.4 for GC and GF breads, respectively.

Butter (composition in 100 g: Energy: 751 kcal, Total fat: 83 g, saturated fat: 59 g, total carbohydrates: <0.5 g, sugar: <0.5 g, protein: 0.6 g, salt: <0.01 g) and mayonnaise (composition in 100 mL: Energy: 614 kcal, total fat: 68 g, saturated fat: 8.1 g, total carbohydrates: 0.6 g, sugar: <0.5 g, protein: 0.8 g, salt: 1.1 g) were added to breads at approximately 12% w/w. These spreads were selected due to the different impact they were expected to have on assisting bolus formation. Butter, a fat based product (water in oil emulsion), was expected to increase the degree of lubrication while mayonnaise, an oil-in-water emulsion, was expected to increase lubrication and moisture content of the food bolus.

[figure not shown]

Figure 1. Sample configuration: A. two stacked cylinders of bread without spread. B. two stacked cylinders of bread with spread (either butter or mayonnaise).

1.3. Test Sessions

Participants attended 2 sessions of approximately 30 min each. The first session was designed for video recording and the second session for the evaluation of texture attributes and collection of food bolus. Participants received detailed information about the test procedure but they were not informed that the objective of the study was to compare GF and GC breads. The sessions were carried out in a sensory room at 20 °C and under normal light conditions.

1.3.1. Video recording

A digital camera (Logitech C920 PRO HD webcam, resolution 1080p/30fps) was positioned approximately 50 cm from the participant's face. Participants evaluated a total of 7 samples from which the first was a test sample used to familiarize the participants with the procedure. Samples were served in randomized order. Participants were instructed to place the whole sample in the mouth (e.g. single bite) and to chew naturally until the bolus was ready for swallowing. Participants were asked to maintain the head straight to the camera, and not to block their mouth or face with their hand while eating. Between samples, participants rinsed the mouth with water.

Videos were decoded using the behavioral annotation software ELAN (version 4.9.1; Max Planck Institute for Psycholinguistics). A coding scheme was developed (Forde et al., 2013; Bolhuis et al., 2014) to record the frequency counts of chews and swallows. Measures of total eating duration (s) (i.e. starting from the moment the sample was placed in the mouth until the final swallow) were directly extracted from the videos. Coding was done by two researchers working independently.

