1.3.2. Check-all-that-apply (CATA) test and bolus collection

During the second session, participants evaluated again the samples (n = 7): a test sample used for familiarization followed by the 6 evaluated samples in randomized order. Participants were instructed to

place the whole sample in the mouth and to chew naturally. After 5 chewing cycles, participants were asked to check all the attributes that describe the texture sensations perceived in the beginning of mastication. A list with attributes and their definitions were provided to guide the participants (Table 2). Participants could also indicate texture attributes not listed. Participants proceeded with chewing until the swallowing point, where they checked again all the attributes that characterize the texture sensations perceived at the end of mastication. The food bolus was then spat in a container, which was kept close to prevent water evaporation. Between samples, participants rinsed the mouth with water.

Table 2: Texture attributes and definitions used for the CATA test.

Attribute	Definition
Hard	Sensation that describes the resistance to being deformed by teeth during chewing.
Soft	The bread has a tender texture, easy to crush when chewing.
Compact/dense	The bread has a tight or little porous structure
Spongy	The bread has a light and porous structure
Crumbly	The bread is easy to disaggregate in crumbs and breaks down rapidly
Pasty	Sensation that describes the formation of a dough of the bolus
Dry	Sensation that describes the absence of moisture in mouth when chewing and the difficulty to moisturize the bread
Sticky/Adhesive	Sensation that describes the adhesion of the bolus to teeth and oral cavity during chewing
Sandy	Sensation that describes the presence of particles in oral cavity which tend to scratch the tongue and throat

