1.5. Data analysis

Statistical analyses will be performed using XLSTAT (Addinsoft, France). Normality of continuous variables will be checked through the Kolmogorov-Smirnov test. Two-way ANOVA tests will be used to check for the effect of type of bread (2 conditions: with/without gluten) and the effect of spread (3 conditions: no spread, butter and mayonnaise) on number of chews, number of swallows, eating duration and bolus properties (saliva content). Interactions between bread and spread will be included in the analysis/model. A post-hoc test will be used for evaluating differences between values. A *p*-value lower than 0.05 will be considered statistically significant, but notable trends will also be reported and discussed. Correlation coefficients (*r*) will be calculated to explore the correlation between oral processing parameters (number of chews, number of swallows, eating duration), bread texture (hardness) and bolus properties (saliva content).

For the CATA test, frequency of mention for each term will be determined by counting the number of participants that used that term to describe each sample. Cochran's Q test will be carried out for each of the terms to detect differences in participants' perception of the evaluated samples.

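### The ANOVA for the six consecutive tastings has no serving-position or preceding-sample term, so any drift inflates the error and any spread carry-over slightly shifts the spread-versus-none contrast

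*Combined protocol and SAP*

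**What the plan says.** Section 1.2 sets out the design: "A 2x3 full factorial design was used with 2 white sandwich breads", crossed with no spread, butter and mayonnaise. That gives six samples, and every participant receives all of them in each session. Section 1.1: "A total of 20 subjects were recruited for this study". Section 1.3: "Participants attended 2 sessions of approximately 30 min each".

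On order, section 1.3.1 says "Participants evaluated a total of 7 samples from which the first was a test sample used to familiarize the participants with the procedure", and then "Samples were served in randomized order". Section 1.3.2 has the same structure for the second session. On washout, both sections give only this: "Between samples, participants rinsed the mouth with water". No minimum interval is stated, nor whether orders were balanced for position or predecessor.

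On analysis, section 1.5 plans two-way ANOVAs of chews, swallows, eating duration and saliva content on bread and spread, adding: "Interactions between bread and spread will be included in the analysis/model". It names no participant, serving-position or preceding-sample term.

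**The concern.** Repeated tasting in one sitting can disturb the comparison in two ways.

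- **Drift.** If chewing or salivation changes steadily over the session through fatigue or habituation, and position is not modelled, the change goes into the residual and the tests lose precision.
- **Carry-over.** Both spreads are rich in fat (butter 83 g per 100 g, mayonnaise 68 g per 100 mL) and were chosen for their expected effect on bolus formation. For instance, "mayonnaise, an oil-in-water emulsion, was expected to increase lubrication and moisture content of the food bolus". If some of that effect outlasts the rinse, the next sample is affected. Because each sample is served once per session, randomisation does not give plain and spread samples the same mix of predecessors.

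Precision is at stake for all contrasts. A small systematic shift is at stake for spread versus no spread, one of the two factors under test.

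**Working it through.** The plan states no sample-size, variance, drift or carry-over figure, so there is nothing of its own to reproduce.

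**Inputs from the documents.** 20 participants; 6 evaluated samples per session (2 breads x 3 spreads, so 2 without and 4 with spread); randomised order; model terms bread, spread and bread x spread.

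**Assumed inputs.** Linear drift d of 0 to 0.3 within-person SD per position; within-person SD 1; between-person SD 1 where it matters; direct spread effect 1; a carry-over L common to both spreads; no carry-over from the familiarisation sample.

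**Carry-over.** A sample has an evaluated predecessor with probability 5/6.
- No-spread sample: 4 of the other 5 carry a spread, so P(preceded by spread) = 5/6 x 4/5 = 2/3.
- Spread sample: 3 of the other 5 do, so P = 5/6 x 3/5 = 1/2.
- Shift in spread-minus-none = L x (1/2 - 2/3) = -L/6. With L = 0.3 of the direct effect, 0.3/6 = 0.05, or 5%.
- Butter versus mayonnaise is shifted only if their carry-overs differ, by -(L_butter - L_mayo)/6.
- For either bread, P(preceded by spread) = (2/3 + 1/2 + 1/2)/3 = 5/9, so spread carry-over cancels from the bread contrast.

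Enumerating all 720 orders confirms these probabilities. Simulated mean estimates with n = 20 and a true contrast of 1.00:

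| L | Bread and spread terms only | Theory, 1 - L/6 | With participant, position and preceding spread |
|---|---|---|---|
| 0.25 | 0.957 | 0.958 | 0.996 |
| 0.5 | 0.919 | 0.917 | 1.003 |
| 1 | 0.838 | 0.833 | 1.002 |

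Adding participant and position without the preceding-spread term leaves the estimate at 0.919 for L = 0.5.

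**Drift.** Positions 1 to 6 have sum of squares 17.5 about their mean.
- Participant in the model: the residual variance factor is 1 + (17.5/5)d² = 1 + 3.5d². At d = 0.2 it is 1.14, and SE rises by √1.14 - 1 = 6.8%. At d = 0.3 it is 1.315, and SE rises by 14.7%.
- ANOVA as written: total variance goes from 2 to 2 + (17.5/6)d². At d = 0.2, √(2.117/2) - 1 = 2.9%. At d = 0.3, √(2.2625/2) - 1 = 6.4%.
- With drift alone, the simulated spread contrast stayed at 0.994 to 1.004, so there is no bias.

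**Effect and cost of the terms.**
- With participant in the model, the mean SE of the bread effect without and with linear position is 0.1817 and 0.1827 at d = 0 (0.1827/0.1817 = 1.0055, a cost of about 0.5%), 0.1947 and 0.1833 at d = 0.2, and 0.2087 and 0.1832 at d = 0.3.
- For the spread contrast with no drift or carry-over, SE goes from 0.193 with participant only to 0.204 with position and preceding spread added, about 6%. That run used categorical position and separate butter and mayonnaise indicators. A linear position and one yes/no indicator use fewer degrees of freedom, so 6% is a cautious figure for them.
- Leaving participant out raises the reported SE of the spread contrast from 0.193 to 0.272.

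**The case against.** The strongest reply is that randomisation already deals with order, and that carry-over is only supposed. Much of this stands.

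- A reader might infer that drift biases the bread or spread effect. It does not. Chance imbalance in mean position (SD √(3.5 x 2/3 / 20) = 0.34 positions between breads) is ordinary random error that the SE reflects. A position term is a gain in precision, not a correction of bias.
- A reader might infer that residual fat does lubricate the next bite. The documents do not show this. Section 1.2 speaks of lubrication of the bolus being chewed. There is a water rinse, about 30 minutes are allowed for seven single bites, and the bolus is spat out in the second session.
- A reader might infer that the comparison of the two breads, which section 1.3 gives as the study's objective, is compromised. Spread carry-over leaves it unbiased.
- A reader might take the 7% and 15% as the loss under the ANOVA as written. They presuppose a participant term, which section 1.5 does not name.
- A reader might infer that unbalanced orders were used and that a Williams square would have cured the problem. The text says only that order was randomised, which does not exclude balancing. In a Williams square, too, plain bread follows a spread in 4 of 6 sequences and spread bread in 3 of 6, so the unadjusted shift is still -L/6.

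What remains is that the predecessor asymmetry is exact, does not shrink with more participants, and can be examined only with a term that the plan lacks.

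**Conclusion.** The point holds as a modest improvement to the analysis. With linear drift of 0.2 to 0.3 within-person SD per position, leaving out position costs about 7% to 15% in SE with participant modelled, or about 3% to 6% in the ANOVA as written with equal variance components. A common spread carry-over L shifts spread versus none by -L/6. If carry-over acts in the same direction as the direct effect and is no larger than it, this weakens the spread effect and does not create a false one. The sizes of drift and carry-over are assumptions, and either could be nil. Omitting participant has a larger effect on the reported SE than drift of this size, so the two should be settled together.

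**What to change.** In section 1.5, for chews, swallows, eating duration and saliva content:

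1. Add participant and linear serving position (1 to 6) to bread, spread and their interaction. Take position from the session in which the outcome was measured: the video session for chews, swallows and duration, and the bolus session for saliva content.
2. Prespecify a sensitivity analysis that adds an indicator for whether the preceding sample had a spread (yes/no). Only this term removes the carry-over shift. The familiarisation sample's identity is not stated, so say how position 1 is coded: from that sample if it is known, otherwise with a separate first-position indicator.

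**Cost.** Participant uses 19 degrees of freedom (error 120 - 6 = 114 falls to 95), and linear position uses one more (94). Position makes SE about 0.5% larger if there is no drift. The sensitivity analysis makes the SE of the spread contrast about 6% larger if there is no carry-over, which is why it should not be the primary model. No new data are needed if the serving orders were recorded. The documents do not say so, and this should be confirmed first.

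No change to the serving design is proposed: the sessions are described as already held, and a Williams square would leave the same shift when unadjusted.

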1.3.2. Check-all-that-apply (CATA) test and bolus collection

During the second session, participants evaluated again the samples (n = 7): a test sample used for familiarization followed by the 6 evaluated samples in randomized order. Participants were instructed to

place the whole sample in the mouth and to chew naturally. After 5 chewing cycles, participants were asked to check all the attributes that describe the texture sensations perceived in the beginning of mastication. A list with attributes and their definitions were provided to guide the participants (Table 2). Participants could also indicate texture attributes not listed. Participants proceeded with chewing until the swallowing point, where they checked again all the attributes that characterize the texture sensations perceived at the end of mastication. The food bolus was then spat in a container, which was kept close to prevent water evaporation. Between samples, participants rinsed the mouth with water.

Table 2: Texture attributes and definitions used for the CATA test.

Attribute	Definition
Hard	Sensation that describes the resistance to being deformed by teeth during chewing.
Soft	The bread has a tender texture, easy to crush when chewing.
Compact/dense	The bread has a tight or little porous structure
Spongy	The bread has a light and porous structure
Crumbly	The bread is easy to disaggregate in crumbs and breaks down rapidly
Pasty	Sensation that describes the formation of a dough of the bolus
Dry	Sensation that describes the absence of moisture in mouth when chewing and the difficulty to moisturize the bread
Sticky/Adhesive	Sensation that describes the adhesion of the bolus to teeth and oral cavity during chewing
Sandy	Sensation that describes the presence of particles in oral cavity which tend to scratch the tongue and throat

1.4. Moisture and saliva content

After collection, boluses were immediately transferred to aluminum dishes, weighed and dried for 24 h at 72 °C in a vacuum oven. After drying, samples were cooled in a desiccator for 10 min and subsequently weighed. The following equation was used to calculate bolus moisture content (MC) on a wet weight basis:

$$MC (\%) = \frac{(w_0 - w_1)}{w_0} \times 100$$

where w_0 is the weight of the sample before drying and w_1 is the weight after drying.

Bolus moisture content on a dry weight basis was calculated using:

$$MCdb = \frac{(w_0 - w_1)}{w_1}$$

The same procedure was followed to determine the moisture content of the 6 bread samples. For that, samples at the same dimensions as served to participants and containing the same proportion of butter or mayonnaise was cut in small pieces weighed and dried for 24 h at 72 °C in a vacuum oven.

Saliva content (SC) per gram dry food was determined by subtracting the moisture content on a dry weight basis of the product from the moisture content on a dry weight basis of the bolus (MCdb).

The rate of saliva incorporation (g/min) was calculated by dividing the saliva content (SC) by eating duration time. These calculations are based on the assumption that the bolus will be fully expectorated.

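### Saliva content is scaled to dry food including the spread, so its spread contrast does not show whether the amount of saliva changed; the saliva rate also carries the wrong unit

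*Combined protocol and SAP*

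**What the plan says.** Section 1.4 defines the outcome: "Saliva content (SC) per gram dry food was determined by subtracting the moisture content on a dry weight basis of the product" from the corresponding value for the bolus. The product values come from "samples at the same dimensions as served to participants and containing the same proportion of butter or mayonnaise", so the reference for a spread sample is bread plus spread. Each bolus is weighed before drying (w0) and after drying (w1), and the calculations assume that the whole bolus is spat out.

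Section 1.2 says the spreads "were added to breads at approximately 12% w/w", without saying whether the base is the bread or the total. It also says that "the average weight of two stacked cylinders was 5.1 ± 0.2 and 5.7 ± 0.4 for GC and GF breads, respectively".

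Section 1.5 tests bread type, spread and their interaction by two-way ANOVA. SC is the only bolus outcome it names.

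Section 1.4 also defines a rate: "The rate of saliva incorporation (g/min) was calculated by dividing the saliva content (SC) by eating duration time". The only definition of eating duration is in section 1.3.1, from the video, "starting from the moment the sample was placed in the mouth until the final swallow". Section 1.3 separates the two measurements: "The first session was designed for video recording and the second session for the evaluation of texture attributes and collection of food bolus".

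**The concern.** Subtracting the product value removes the spread's own water from the numerator. It does not remove the spread's solids, which are mostly fat, from the denominator. If a participant adds the same saliva to a plain bite and to a buttered bite, SC is lower for the buttered one by construction.

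Spread is one of the two design factors. A lower SC with spread would be a true statement about bolus composition, but it would not show that less saliva was added, and a real increase in saliva could appear as no change in SC. The plan has no second measure to separate these. If the correlations in section 1.5 are pooled over spread conditions, which the section does not say, the same shift enters them.

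The rate has the same denominator and a unit that does not match its formula. It also appears to combine a timed, swallowed bite from session 1 with a bolus from session 2. That bolus was spat out, and its chewing was interrupted for ratings: "After 5 chewing cycles, participants were asked to check all the attributes that describe the texture sensations perceived in the beginning of mastication".

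**Working it through.** The plan gives no SC value, variance or sample size calculation, so there is no figure to reproduce.

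**1. What SC measures.** Let W be product water, D dry bread, S dry spread and V saliva water, ignoring saliva solids. Then SC = (W + V)/(D + S) - W/(D + S) = V/(D + S).

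**2. Inputs (section 1.2).** Label values are taken per 100 g and weights in grams.
- GC solids: 3.9 + 48.4 + 4.5 + 8.5 + 1.25 = 66.55%. D = 5.1 × 0.6655 = 3.394 g.
- GF solids: 5.0 + 44.5 + 6.0 + 3.0 + 1.4 = 59.9%. D = 5.7 × 0.599 = 3.414 g.
- Butter solids: 83.6-84.1 g per 100 g (carbohydrate is given only as below 0.5 g).
- Mayonnaise solids: 68 + 0.6 + 0.8 + 1.1 = 70.5 g per 100 mL. Density is not given; at an assumed 0.9-1.0 g/mL this is 78.3-70.5 g per 100 g.
- Spread mass as a fraction of bread, p: 0.12 if the base is bread, 0.12/0.88 = 0.136 if the base is the total.

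Counting fibre separately from carbohydrate fits the label energy: 9 × fat + 4 × carbohydrate + 2 × fibre + 4 × protein gives 271.7 kcal for GC (stated 272) and 247.0 for GF (stated 247).

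**3. Change in SC at equal saliva per bite: -S/(D + S).** Example, GC with butter, p = 0.12: S = 0.12 × 5.1 × 0.836 = 0.512 g, and 0.512/(3.394 + 0.512) = 13.1%.

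| Spread | GC | GF |
|---|---|---|
| Butter | 13.1-14.7% lower | 14.3-16.1% lower |
| Mayonnaise | 11.3-13.8% lower | 12.4-15.1% lower |

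If fibre were already inside carbohydrate, the ranges over both breads would be about 14.0-17.6% for butter and 12.0-16.4% for mayonnaise (density 0.91-1.0).

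**4. The same effect reversed: S/D.** Saliva per bite would have to rise by 15-19% with butter, or 13-18% with mayonnaise, for SC to stay level.

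**5. Bread contrast.** The GF/GC ratio of total dry mass is 3.414/3.394 = 1.006 plain and about 1.02 with either spread. At equal saliva this moves SC by about 0.6% and 2%.

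**6. Scale against n = 20.** Averaged over the two breads, the shift is 11.8-15.4% of the plain mean. For a paired comparison, t(0.975, 19)/√20 = 2.093/4.472 = 0.468. An observed difference of this size alone would give unadjusted p < 0.05 if the SD of paired differences were below 0.118/0.468 = 25% to 0.154/0.468 = 33% of the plain mean. This is a threshold only: the documents do not give the SD, and a multiplicity-adjusted post-hoc test would need a smaller one.

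**7. Rate.** SC is in g per g dry food, so SC/duration is g per g dry food per min. The factor that converts it to g/min is the dry mass of the bite: about 3.4 g plain and roughly 3.8-4.1 g with spread. As an illustration with an assumed 3 g of saliva and 30 s, GC plain gives SC = 3/3.394 = 0.884 and SC/0.5 = 1.77, while the amount per time is 3/0.5 = 6.0 g/min.

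**8. Amount of saliva from data already planned.** SC × w1 = (w0 - w1) - (product MCdb × w1), which is bolus water minus product water. Under full expectoration this is the saliva in that bite.

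**The case against.** SC is openly defined per gram of dry food, and section 1.5 lists it as a bolus property. Nowhere does the plan say that a spread effect on SC will be read as a change in the amount of saliva. That stands: the main point concerns what the contrast can support, and is not an error in the ANOVA.

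Equal saliva per bite is only one possible null. A spread bite is about 12-14% heavier, so more saliva per bite may simply follow a larger bite. Under equal saliva per gram of dry food, SC does not shift at all. This also stands, and it is why saliva per bite should sit beside SC and not replace it.

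The rate enters no ANOVA or correlation in section 1.5, and section 1.4 does not name the session that supplied the duration. Use of session 1 is an inference, though a strong one, because no timing is described for session 2. What remains is that the stated unit does not follow from the stated formula.

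A reader might infer that SC is invalid, that any spread effect on it is an artefact, or that the gluten comparison is biased. The documents support none of these: SC is a legitimate composition measure, the shift is conditional on one null, and the dry masses of the two breads are nearly equal.

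**Conclusion.** The point holds in a limited form. The spread contrast in SC describes bolus composition and cannot by itself show whether the amount of saliva changed. At equal saliva per bite, SC is about 13-16% lower with butter and 11-15% lower with mayonnaise. These are not predictions of the result. They rest on labels per 100 g, weights in grams, the same bread mass with and without spread, complete drying, a mayonnaise density of 0.9-1.0 g/mL, and either reading of the 12%.

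The rate is wrong as written. Values printed as g/min would be about 3.4 to 4 times too low, by a factor that differs between plain and spread samples. It would go too far to infer that this affects a listed test: only a reported descriptive value is at issue. Nor do the documents establish that session 1 supplied the duration; they leave it unstated.

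The first part should be dealt with before analysis, because it limits what one of the two design factors can say. The second is a correction of unit and source.

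**What to change.** (a) Keep SC as the planned outcome and interpret it as bolus composition. In section 1.5 add: *Saliva per bite, SC × w1, will be analysed as a supplementary outcome in the same model and reported beside SC. Any statement that a spread changes the amount of saliva will rest on this measure.* As a sensitivity check against incomplete expectoration, repeat it with SC × mean served dry mass of the product, where served dry mass is mean served weight / (1 + product MCdb).

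(b) In section 1.4, either compute the rate as saliva per bite divided by duration in minutes, which gives g/min, or relabel it g per g dry food per min. In either case state which session supplied the duration and that the bolus came from session 2. Changing the numerator does not remove a mismatch between sessions.

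Cost: one extra derived outcome and a small text correction. SC × w1 uses weights already taken and needs neither served weights nor the base of the 12%. Section 1.5 is written in the future tense, so the measure can be named in advance. Downsides: saliva per bite partly reflects the heavier spread bite, and SC × w1 is too low if bolus is lost. The sensitivity check needs mean served weights of the spread samples and uses one constant per product, so it leaves bite-to-bite weight variation uncorrected: 0.2/5.1 = 4% for GC and 0.4/5.7 = 7% for GF, if the ± values are SDs.

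### The saliva incorporation rate divides saliva in a bolus collected at the swallowing point by a time that runs on to the final swallow, so the two parts of the ratio cover different windows

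*Combined protocol and SAP*

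**What the plan says.** Section 1.4 states that the rate, labelled g/min, was "calculated by dividing the saliva content (SC) by eating duration time". Saliva content (SC) is the bolus moisture on a dry basis minus the product's own moisture on the same basis. The only assumption stated for these calculations is that the whole bolus is expectorated.

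Section 1.3.1 takes eating duration from the session 1 videos, "starting from the moment the sample was placed in the mouth until the final swallow". The same coding scheme was set up "to record the frequency counts of chews and swallows".

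Section 1.3.2 describes how the bolus was obtained in session 2. After a first checklist at five chews, "Participants proceeded with chewing until the swallowing point, where they checked again all the attributes". Then: "The food bolus was then spat in a container, which was kept close to prevent water evaporation".

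Section 1.3 confirms that the two measurements come from different occasions: "The first session was designed for video recording and the second session for the evaluation of texture attributes and collection of food bolus".

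Section 1.5 names number of chews, number of swallows, eating duration and saliva content as ANOVA outcomes. It does not name the rate there or among the correlations.

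**The concern.** A rate of saliva uptake makes sense when the saliva and the time refer to the same interval. Here the saliva is what the bolus has taken up when it is ready to be swallowed. The time also covers the first swallow, any later chewing of residue and every later swallow.

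The plan allows for more than one swallow per sample, since it counts swallows and tests whether the count differs by bread and spread. Section 1.2 adds that the spreads were chosen because they were expected to affect bolus formation differently. A condition that leaves more residue and takes longer to clear would show a lower rate with no change in salivation. A comparison of rates between breads or spreads could then partly reflect differences in clearing time.

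**Working it through.** The plan gives no eating duration, swallow count or saliva rate, so there is no figure to reproduce. The check is algebraic, with assumed times.

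**Inputs**
- Numerator: SC at the swallowing point (sections 1.3.2 and 1.4).
- Denominator: time from placement in the mouth to the final swallow (section 1.3.1).
- t1, the time to the first swallow: not in the documents; assumed 15 to 40 s.
- g, the time from first to final swallow: not in the documents; taken as k later swallows of c seconds each, with c assumed 2 to 6 s.

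**Step 1. End-point mismatch alone.** The plan's rate divided by a time-matched rate is

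[SC/(t1+g)] / [SC/t1] = t1/(t1+g).

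SC cancels, so its size and units do not matter. The proportional lowering is 1 − t1/(t1+g).

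- t1 = 25 s, g = 4 s (one later swallow): 25/29 = 0.86, a lowering of 14%.
- t1 = 25 s, g = 8 s (two later swallows): 25/33 = 0.76, a lowering of 24%.
- One later swallow over the whole assumed range: from 40/42 = 0.95 to 15/21 = 0.71, a lowering of 5% to 29%.
- No later swallow: ratio 1, no error.

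**Step 2. Effect on a comparison.** Take two conditions with the same true rate and t1 = 25 s, one with g = 4 s and the other with g = 8 s. Their reported rates stand in the ratio (25/33)/(25/29) = 29/33 = 0.88, an apparent difference of 12%.

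**Step 3. Does the error follow the swallow count?** Not necessarily. With c = 4 s:
- t1 = 15 s and one later swallow: 15/19 = 0.79.
- t1 = 40 s and two later swallows: 40/48 = 0.83.

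The condition with more later swallows is lowered less. What matters is the share of eating duration after the first swallow.

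**Step 4. Is the net error downward?** In session 2 both checklists are completed before the bolus is spat out. Suppose this adds p seconds of holding, during which saliva enters at a fraction f of its chewing rate. The ratio becomes (t1+f·p)/(t1+g). With t1 = 25 s and g = 4 s:
- p = 10 s, f = 0.5: 30/29 = 1.03.
- p = 20 s, f = 1: 45/29 = 1.55.

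The holding time is not in the documents either. Under these assumptions it offsets or outweighs the end-point error.

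**The case against.** The strongest objection is that no planned test uses the rate. Section 1.5 analyses saliva content, chews, swallows and eating duration, and the mismatch touches none of them. This stands, and it makes the point minor. The rate is still a defined quantity, and any comparison drawn from it carries the error.

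A reader might infer that the rate is understated, and understated most in the conditions needing the most swallows to clear. The documents support neither inference. They give no times or counts by condition, step 3 shows that the ordering can reverse, and step 4 shows that the net error can be upward. The checklist hold is, however, a second mismatch of unknown length. It does not justify the wrong end point, and nothing in the documents suggests that the two cancel equally across conditions.

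It can also be said that the problem belongs to the use of two sessions: had the session 2 bolus been timed until it was spat out, there would be no final swallow in the denominator. That is correct for that particular remedy. The documents describe no timing in session 2, so with the session 1 time as defined the mismatch remains.

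Finally, moving the end point alone need not bring the rate closer to the truth. In the example with a 10 s hold at half rate, the ratio goes from 30/29 = 1.03 to 30/25 = 1.20. This stands as a reason to disclose the hold alongside the change.

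**Conclusion.** The concern holds in a limited form. Sections 1.3.1, 1.3.2 and 1.4 together give a rate whose numerator stops at the swallowing point and whose denominator runs to the final swallow. Taken alone, this lowers the rate by 1 − t1/(t1+g), an amount that may differ by bread and spread. The 14% example and the 5% to 29% range rest wholly on assumed times. The net direction and the ordering of conditions cannot be determined from the documents. The harm is confined to the rate and comparisons made from it. Severity is minor; the end-point mismatch itself is plain from the text.

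**What to change.** In section 1.4, define the rate's denominator as the time from placing the sample in the mouth to the first swallow, read from the existing session 1 videos. Keep total eating duration to the final swallow as its own outcome, unchanged.

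Add a stated limitation: SC comes from a separate session in which the bolus stayed in the mouth during two checklists, so the rate remains approximate and could err in either direction.

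The cost is one more time point per video. Section 1.3.1 describes swallow counts, not stored swallow times, so up to 20 × 6 = 120 videos may have to be re-read. No new participant data are needed. The change removes only the end-point part of the error. If the videos are not re-read, the mismatch of end points should be stated as a limitation too.
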